Study Protocol

Official Title: Telemedicine for Reach, Education, Access, and Treatment-Ongoing (Treat-On) Study

ClinicalTrials.gov ID (NCT number): NCT04107935

Document Date: 7-24-23

Study Protocol

This was a 12-month non-randomized trial that evaluated TREAT-ON prospectively and compared it to a retrospective in-person diabetes self-management education and support (DSMES) program. Both programs were offered at Federally Qualified Health Centers (FQHCs) providing care to mostly medically underserved, underinsured and uninsured in rural communities located across three of the most distressed counties in Western Pennsylvania. The University of Pittsburgh Medical Center (UPMC) services extend across the region, and based on UPMC Health Plan data, approximately 1,300 adult patient-members with T2DM received care at the participating FQHCs (58% female, mean age 58y, >75% Medicare/Medicaid) at the time of the study. The FQHCs were chosen because they offered the UPMC Health Plan's *Diabetes High Risk Initiative*, an insurer-based DSMES program, to patient-members with a diagnosis of T2DM and considered to be at "high risk" for diabetes-related problems (Zupa et al, 2019). The purpose of this study was to compare TREAT-ON, an enhanced telehealth version of the *Diabetes High Risk Initiative*, to matched controls who had already completed the *Diabetes High Risk Initiative* in person. This study was approved by the University of Pittsburgh's Institutional Review Board.

Models for DSMES

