The DSMES intervention was initiated by the DCES where a comprehensive assessment (review of clinical needs, history, psychosocial needs and barriers, current therapy, nutrition, activity, risk factors, coping strategies, problem solving skills, with attention to health literacy and cultural influences) was conducted. Based on the assessment, the DCES collaborated with the patient (and PCP) to establish an individualized treatment plan with medication recommendations and self-management goal(s), as well as provide DSMES. Building on this, ongoing management and support was delivered to the patient (and their caregiver if invited) via

videoconferencing. As part of ongoing support, the DCES was available upon need and request to the patient over the 12-month period, the DCES had the opportunity to assess an individual's progress towards meeting their self-management goals, address challenges and barriers that may be impeding progress, and reinforce self-care behaviors, problem solving-skills and coping strategies. Consistent with the patient empowerment-oriented approach, a patient-centered model tailored to meet the patient's needs (Anderson et al, 1995) the DCES collaborated with the patient to determine content for discussion, number, length and frequency of follow-up sessions. Content was in keeping with the National Standards for DSMES (Davis et al, 2022).

Recruitment, Enrollment and Training

Study patient participants were identified through the UPMC Health Plan population health reports and were invited to participate by a DCES at a participating FQHC if the individual met the "high risk" conditions (Zupa et al, 2019). Participating patients were consented and introduced to the TREAT-ON model and familiarized with the telemedicine videoconferencing technology by the DCES and health system's technology staff.

Outcome Measures

Data were collected at baseline and 3, 6 and 12 months for all outcome measures except for intervention acceptability, which was only assessed at follow-up. HbA1c served as the primary outcome and clinical measure of improved DM management. HbA1c values were obtained from the patient's medical record. Behavioral and psychosocial outcomes were assessed with validated self-report instruments.

[figure not shown]

Figure. Overview of TREAT-ON Model of Care

References

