Statistical Analysis Plan

Official Title: Telemedicine for Reach, Education, Access, and Treatment- Ongoing (Treat-On) Study

ClinicalTrials.gov ID (NCT number): NCT04107935

Document Date: 7-24-23

Statistical Analysis

We expected to enroll 50 participants into the intervention and compare to a retrospective usual care group (control) that was also anticipated to include 50 participants. Control participants were identified from a pre-existing data set.

A control group was selected from individuals who had previously participated in the *Diabetes High Risk Initiative*. Propensity score matching was used to form pairs of intervention and control participants. Specifically, a greedy matching procedure with a matching caliper of 0.2 of the standard deviation of the logit of the propensity score was used to create pairs. For a participant in the intervention group, the closest control participant within the specified caliper distance was selected for matching. Factors selected *a priori* for inclusion in the propensity score included several covariates known to be possible correlates of HbA1c: race (White and non-white), ethnicity, age, body mass index (BMI), baseline HbA1c, and gender. Standardized mean differences were then calculated to examine the balance between the two exposure groups. Variables with standard mean differences <0.1 were considered to be balanced.

Baseline characteristics of the intervention and control group as well as those who met and did not meet their diabetes self-management goal were presented using measures of central tendency (median, interquartile range) for continuous variables and number and percentage for categorical variables. Comparisons were made using the Wilcoxon rank sum and chi-sq tests. To examine the change in HbA1c over time, mixed model regression was employed. Since the baseline characteristics achieved a good balance, those variables were not entered into the propensity score matched model.

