A secondary analysis, using only the participants in the intervention group (n=42), was performed to examine the difference in HbA1c and survey scores for self-care, diabetes distress, empowerment, and the TUQ between those that met their diabetes self-management goal versus those that did not. Similar analyses methods were used except the mixed models were adjusted for age, race, BMI, gender. P-values <0.05 was considered significant. Finally, acceptability and feasibility of the intervention were examined at the end of the study (at month 12) using descriptive statistics. All analyses were carried out using SAS 9.4 (Carey Institute Inc).

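### Observed balance is not a sufficient reason to leave baseline HbA1c out of the only between-program HbA1c model; if baseline is an unconstrained response, the interval is wider than it needs to be

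*SAP*

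**What the plan says.** The SAP (Statistical Analysis) describes the design step as follows: "Propensity score matching was used to form pairs of intervention and control participants". The score uses "race (White and non-white), ethnicity, age, body mass index (BMI), baseline HbA1c, and gender", and the balance rule is "Variables with standard mean differences <0.1 were considered to be balanced". For the outcome it says "To examine the change in HbA1c over time, mixed model regression was employed", and then "Since the baseline characteristics achieved a good balance, those variables were not entered into the propensity score matched model". Observed balance is the only reason given, and no other between-program HbA1c model is described.

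The Protocol (Outcome Measures) makes HbA1c the primary outcome. On timing it says "Data were collected at baseline and 3, 6 and 12 months for all outcome measures", with an exception only for acceptability. For the secondary analysis within the intervention group (n=42), the SAP says "Similar analyses methods were used except the mixed models were adjusted for age, race, BMI, gender".

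The SAP does not say whether baseline HbA1c is a response or a covariate, whether group means are constrained equal at baseline, or whether the matched pairs enter the model.

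**The concern.** Balance and adjustment do different jobs. Balance on baseline HbA1c limits confounding by it. It does not remove the outcome variance that baseline explains, and it does not tell the model that the groups start level.

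A model of change over time, with HbA1c measured at baseline and three later visits, most naturally has baseline among its responses. Without an equal-baseline constraint, such a model treats the two baseline means as free. The SE of the change contrast then includes sampling error for a baseline gap that matching has already made small.

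What is at stake is precision on the primary outcome, in a study with 42 intervention participants. Baseline HbA1c is already held for every matched participant, because the propensity score needs it.

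**Working it through.** **Inputs from the documents.** Six matching variables including baseline HbA1c; standardized mean difference (SMD) limit 0.1; visits at baseline, 3, 6 and 12 months; 42 intervention participants; significance level 0.05. The plan gives no SD, correlation, effect size, dropout rate or number of matched pairs, so there is no figure of its own to reproduce.

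**Assumed.** Correlation r between baseline and follow-up HbA1c of 0.3, 0.5, 0.7 or 0.8; ratio k of follow-up SD to baseline SD of 0.8 to 1.5; two-sided testing.

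**Step 1: formula.** With baseline SD s0, follow-up SD s1 and n per group:
- unconstrained change contrast: SE² = (2/n)(s0² + s1² − 2·r·s0·s1)
- baseline-adjusted or equal-baseline contrast: SE² = (2/n)·s1²(1 − r²)

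The brackets differ by (s0 − r·s1)², which is never negative. With complete data the unconstrained SE is therefore never the narrower one, and the two agree only when r·k = 1. The SE ratio is sqrt[(1 + k² − 2rk) / (k²(1 − r²))].

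**Step 2: one case in full.** Take k = 1, r = 0.5 and 42 per group (assumed). Unconstrained: sqrt(2 × 0.5) × sqrt(2/42) = 0.218 SD. Adjusted: sqrt(0.75) × sqrt(2/42) = 0.189 SD. The ratio is 1.155. A four-visit generalised least squares calculation (compound symmetry, complete data, 42 per group) gives the same ratio.

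**Step 3: the range.** Unpaired SE divided by baseline-adjusted SE:

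| k | r = 0.3 | r = 0.5 | r = 0.7 | r = 0.8 |
|---|---|---|---|---|
| 0.8 | 1.41 | 1.32 | 1.26 | 1.25 |
| 1.0 | 1.24 | 1.15 | 1.08 | 1.05 |
| 1.25 | 1.13 | 1.06 | 1.01 | 1.00 |
| 1.5 | 1.07 | 1.02 | 1.00 | 1.02 |

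**Step 4: power.** Given a balanced baseline, the two estimates nearly coincide and only the reported SE differs. A difference with 80% power after adjustment then has power Φ(2.802 − 1.960 × ratio). At k = 1 this is 64.5%, 70.5%, 75.0% and 76.9% for the four values of r. At the worst corner of the table it is Φ(2.802 − 1.960 × 1.411) = Φ(0.036), about 51%. Where the ratio is 1.00 it stays at 80%.

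**Step 5: matching, pairs and dropout (all at k = 1).** A simulation used 42 intervention participants, control pools of 60, 100 or 200, pre-match shifts of 0.1 to 0.5 SD, and greedy matching with the SAP's caliper. It kept matched sets with baseline HbA1c |SMD| below 0.1. Results in order of r = 0.3/0.5/0.7/0.8:
- unpaired SE over adjusted SE: 22–24/14–15/8/5% larger
- with pairs modelled: 17–18/10–12/5–6/3–4% larger; pairs share a propensity score, not a baseline HbA1c, so pairing recovers only part of the excess
- rejection under no effect, nominal 5%: 1.6–2.0/2.3–3.0/3.2–4.1/3.8–4.7% unpaired, and 4.9–5.5% adjusted
- mean bias agrees within 0.003 SD with and without adjustment

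In the four-visit calculation with 40 per group, assumed dropout of 15% lowers the unpaired ratios to 1.209/1.135/1.074/1.047, and 30% lowers them to 1.176/1.114/1.063/1.040.

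**Step 6: residual imbalance.** At k = 1, a baseline SMD at the 0.1 limit moves the change contrast by (1 − r) × 0.1, which is 0.07, 0.05 or 0.03 SD at r = 0.3, 0.5 or 0.7.

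**The case against.** The strongest reply is that this is missing detail rather than a wrong choice. The SAP refers to baseline characteristics without naming baseline HbA1c in that sentence. If baseline is a response, it should not also be a covariate, and with an equal-baseline constraint there is no loss at all. This stands in part. The loss is conditional, and including baseline HbA1c among the omitted variables is an inference from the propensity score list. But the SAP does more than stay silent: it offers balance as its reason for omission, and that reason is insufficient.

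The second reply concerns size, and it stands. Figures for equal SDs look precise, yet k matters as much as r. The Protocol (Models for DSMES) lists HbA1c above 9% among the high-risk criteria. A floor at baseline but not at follow-up tends to push k above 1. As an illustration, if baseline were the top 20–50% of a normal population, with population correlations of 0.3/0.5/0.7/0.8, the excess would be 6–9/4–6/2–3/1–2%. Skewness, or treatment that narrows the follow-up spread, could act the other way.

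Three stronger readings go beyond the documents:
- A reader might infer that the secondary analysis confirms the omission of baseline HbA1c. It is only consistent with it. Those models adjust for age, race, BMI and gender, do not list baseline HbA1c either, and carry no balance argument.
- A reader might infer that the loss is negligible once r reaches 0.7–0.8. At k = 0.8 it is still 25–26%.
- A reader might infer a false-positive or bias problem. The calculations show a conservative test and little bias from baseline HbA1c.

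**Conclusion.** The concern holds in conditional form. The stated rationale is insufficient whichever way the model was built. If baseline HbA1c is an unconstrained response, the SE of the primary contrast is too wide: by 0–41% unpaired over the r and k values considered, and by 5–24% if the SDs are equal. Modelling the pairs or allowing for dropout reduces the excess, and the HbA1c criterion may reduce it further. If group means are constrained equal at baseline, the loss is zero. The documents cannot place the trial within this range, because they give no correlation, SDs, pair count or baseline constraint. The consequence is lost precision, not invalid inference. It matters most if the between-program result was not significant, since an avoidably wide interval may have contributed. The point is worth acting on, with medium confidence.

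**What to change.** State the role of baseline HbA1c and how matched pairs are handled. Whatever the SMDs show, fit the matched mixed model to the 3-, 6- and 12-month values with baseline HbA1c as a covariate, and account for the pairs. The alternative is to keep baseline as a response with equal group means at baseline, saying that equality rests on matching and not on randomisation. Use one or the other, not both. Keep the current model as a sensitivity analysis, and report r and the two SDs so that readers can place the loss in the table.

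Both documents are written in the past tense. If results are already known, label the adjusted model post hoc and report it beside the analysis as planned. The change is one SAP sentence and one model statement, with no new data. It costs a few degrees of freedom and possibly the post hoc label.

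### Does the comparison of participants who met or missed their goal need a stated contrast and a baseline adjustment before it can be used?

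*SAP*

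**What the plan says.** The SAP (Statistical Analysis) describes the main HbA1c model briefly: "To examine the change in HbA1c over time, mixed model regression was employed". It leaves covariates out of that model for a stated reason: "Since the baseline characteristics achieved a good balance, those variables were not entered into the propensity score matched model". The secondary analysis follows: "A secondary analysis, using only the participants in the intervention group (n=42), was performed to examine the difference in HbA1c and survey scores", the comparison being "between those that met their diabetes self-management goal versus those that did not". Its method is "Similar analyses methods were used except the mixed models were adjusted for age, race, BMI, gender".

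Three other places bear on the point. The same SAP section plans a baseline table for the two goal groups, with rank-sum and chi-square comparisons. The Protocol (Outcome Measures) has every outcome collected at baseline, 3, 6 and 12 months "except for intervention acceptability, which was only assessed at follow-up". The Protocol (The TREAT-ON Model) has self-management goals agreed with each patient after the educator's assessment.

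**The concern.** The secondary aim is worded as a difference, which can mean a level at some visit, an average level over visits, or a change. The listed covariates are age, race, BMI and gender; the outcome's own baseline value is not among them. The SAP's reason for omitting baseline variables from the main model is balance after matching. That cannot carry over to goal groups, which are subsets of one arm formed after baseline. The plan also does not say when or how attainment was judged, and it describes no mixed model for the survey scores before this line.

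If people who met their goal tended to start with lower HbA1c, a level contrast without the baseline value would credit attainment with a gap that was there from the start. Two analysts following the text could then report opposite conclusions from the same 42 people.

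**Working it through.** The plan gives no power, SD or effect size for this analysis, so there is no figure to reproduce. The check is a reading of the text, then an illustration on assumed inputs.

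**1. The text.** The secondary method is the earlier method with one stated exception, and the exception concerns covariates only. What carries over for HbA1c is the mixed model for change over time. Baseline is one of the four collected visits, so the ordinary way to fit this has baseline as the first response and a group-by-time contrast. A persistent starting difference then cancels. The level reading is not excluded, but it needs the reader to set aside the reference back to the main method.

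**2. Chance imbalance.** Even if attainment is unrelated to baseline, with a 21/21 split (assumed) the SE of a standardised difference is √(1/21 + 1/21) = 0.309. The chance of exceeding the SAP's 0.1 limit is P(|Z| > 0.1/0.309) = 75% (76% at 14/28, 78% at 10/32). Averaged over such chance gaps, every contrast below still rejects at about 5%.

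**3. A baseline gap that persists.** Assume gap d = 0.5 SD, no difference in change, between-visit correlation ρ = 0.5, two-sided 0.05 and 36 df. Noncentrality is bias / (0.309 × √variance), in SD units.

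| Contrast | Bias | Variance | Noncentrality | Rejects |
|---|---|---|---|---|
| Level at month 12 | 0.5 | 1 | 1.62 | 35% |
| Level, mean of four visits | 0.5 | (1+3ρ)/4 = 0.625 | 2.05 | 51% |
| Change to month 12 | 0 | 2(1−ρ) = 1 | 0 | 5% |
| Month 12, baseline as covariate (approximate) | d(1−ρ) = 0.25 | 1−ρ² = 0.75 | 0.94 | 15% |

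Over ρ from 0.3 to 0.7 the four-visit level figure runs from 63% down to 43%; change stays at 5%. At d = 0.25 the month-12 level contrast rejects 12%.

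**4. A baseline gap that regresses.** If attainment follows the observed baseline value, the gap shrinks to ρd. Change then carries a bias of d(1−ρ) = 0.25 against the group that met its goal: noncentrality 0.25/(0.309 × 1) = 0.81, rejecting 12% (9% to 15% over ρ from 0.7 to 0.3). The baseline-covariate model is now unbiased and rejects 5%. The two models swap places according to a mechanism the documents do not describe.

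**5. Simulation.** Inputs: n=42, SD 1.6, ρ = 0.5, four unrelated covariates, no true effect, attainment correlated 0.2/0.3/0.4 with baseline.

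| Attainment follows | Level, four visits | Change to month 12 | Follow-up mean, baseline covariate |
|---|---|---|---|
| Observed baseline | 12/20/35% | 7/11/16% | 5/5/5% |
| Stable personal level | 23/47/74% | 5/5/5% | 12/21/35% |

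For scale, at an even split the baseline gap is 2√(2/π) × r × SD, so r = 0.4 means 1.596 × 0.4 × 1.6 = 1.02 HbA1c points. The 74% therefore presupposes that the two groups started, and stayed, about a full point apart.

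**6. Disagreement between readings.** Level and change differ on p<0.05 in 18/27/40% of simulated data sets in the first row and 26/47/72% in the second. With no link to baseline at all they still differ in 9%, so only the excess over 9% counts.

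**The case for a change.** The best case for acting is that the remedy is cheap. Naming the contrast takes a sentence, the Protocol says baseline values were collected, and p<0.05 is applied to several outcomes in 42 people. The main section describes a mixed model for HbA1c only, so the pointer to change over time is weaker for the survey scores. The baseline table would let readers see a gap, provided baseline HbA1c is in it, but no rule carries a gap into the model.

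Most of that stands as description. The contrast, the visits and the attainment rule are not written down, and a level contrast that ignores the outcome's baseline value is not ruled out. What does not stand is the step to a needed correction. The model is already adjusted for four covariates. The sound reading is also the one the text points to.

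The additions one might ask for are contestable. Making the baseline-covariate model the rule would exchange one possible bias for another (steps 4 and 5). Requiring both models to agree before drawing a conclusion costs power: at an assumed true difference of 1.0 point, 42% for agreement, with the covariate model averaged over follow-up and change taken to month 12. On equal visits the single models give 47% for change and 57% for baseline covariate at month 12, or 63% and 83% averaged over follow-up.

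It might also be said that the TUQ has no baseline and so forces a level contrast. The documents do not define the TUQ. The SAP lists it among the outcomes compared between goal groups and treats acceptability in a separate sentence, so nothing can rest on that.

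**Conclusion.** No change is called for. This is a gap in detail that an analyst following the SAP would fill sensibly for HbA1c, with a change-over-time mixed model in which baseline is the first visit. Under that reading the false-positive rate in the simulations at ρ = 0.5 is 5% if attainment follows a stable personal level, and 7% to 16% if it follows the observed baseline. The 23% to 74% rates belong to the four-visit level contrast with attainment following a stable level. They depend on assumed values for SD, correlation, split and, above all, a link between individually set goals and HbA1c level that neither document asserts. With no such link every contrast rejects at about 5%.

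The choice between change and baseline covariate is a fair trade-off, since each is unbiased where the other is not. Because attainment was not randomised, no version of the model turns this into more than an association, and the SAP already calls it secondary. The matched comparison of TREAT-ON with its controls does not depend on it. The survey scores are the least specified part, and a report that states which contrast was fitted settles that.

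### The goal-met versus goal-not-met analysis calls each of five outcomes significant at an unadjusted P<0.05, with no hierarchy, adjustment or exploratory label

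*SAP*

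**What the plan says.** The final paragraph of the SAP (Statistical Analysis) begins: "A secondary analysis, using only the participants in the intervention group (n=42), was performed". Its aim was "to examine the difference in HbA1c and survey scores for self-care, diabetes distress, empowerment, and the TUQ". The two groups are the participants who reached their goal and the participants who fell short of it. That is five outcomes and one pair of groups.

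The methods follow those of the main analysis, with the mixed models now adjusted for four covariates. The same paragraph gives the only significance threshold in either document: "P-values <0.05 was considered significant".

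The Protocol (Outcome Measures) names one primary outcome: "HbA1c served as the primary outcome and clinical measure of improved DM management". Neither document carries that priority into the goal-met comparison as a testing order. Neither describes a multiplicity adjustment or calls this comparison exploratory or hypothesis-generating. The one label it carries is that it is secondary.

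**The concern.** A secondary label would do little harm if the results were presented only as estimates. Here it sits beside a rule that turns any P-value under 0.05 into a significant difference. Followed as written, the rule lets any one of five outcomes support a statement that participants who met their goal differed from those who did not. The reader has nothing to tell a leading question from a supporting one, and no prompt to discount a single positive result among five.

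What is at stake is the reading of this within-arm comparison. An isolated, borderline result on one questionnaire could be reported with the same word, significant, as the trial's main HbA1c result. The point does not touch the matched comparison of TREAT-ON with the in-person programme, or the separate question of whether grouping participants by an event after baseline is sound.

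**Working it through.** The documents state no family-wise error rate, power or sample-size derivation, so there is no figure of theirs to reproduce.

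**Inputs from the documents**
- Threshold per test: 0.05 (SAP, final paragraph).
- Number of outcomes: k = 5 (SAP, same paragraph).
- Participants: 42 (same paragraph). This does not enter the error-rate calculation.

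**Assumptions**
- One test per outcome. The SAP does not specify the contrast taken from each mixed model.
- Two-sided tests. The SAP does not say.
- A common correlation between the five test statistics, varied from 0 to 0.9. The documents give none.
- No outcome truly differs between the two groups.

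**Step 1: independent tests.** P(at least one P<0.05) = 1 − (1 − 0.05)^5 = 1 − 0.7738 = 0.226. Under any dependence the upper bound is 5 × 0.05 = 0.25.

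**Step 2: correlated tests.** Simulation of five equally correlated normal test statistics, 2,000,000 draws per setting:

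| Assumed correlation | P(at least one P<0.05) |
|---|---|
| 0 | 22.6% |
| 0.1 | 22.4% |
| 0.3 | 20.9% |
| 0.5 | 18.3% |
| 0.7 | 14.9% |
| 0.9 | 10.2% |

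Even at 0.9 the chance is about twice that for a single test.

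**Step 3: what a false positive would look like (independent tests).** P(exactly one of five) = 5 × 0.05 × 0.95^4 = 0.2036. As a share of all cases with at least one, this is 0.2036 / 0.2262 = 90%. The chance that the smallest P is below 0.01 is 1 − 0.99^5 = 0.049. So the smallest P lies between 0.01 and 0.05 in (0.2262 − 0.0490) / 0.2262 = 78% of such cases. The typical false positive is therefore a single result in that band. With correlated outcomes a lone positive is less dominant.

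**Step 4: effect of an adjustment.** Holm tests the smallest of five P-values at 0.05 / 5 = 0.01. If all nulls are true, its family-wise rate is set by that first step: 0.049 under independence, and at most 0.05 under any dependence.

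**Step 5: price of that adjustment.** Take an assumed even split of 21 and 21, one test, 80% power and the normal approximation. The detectable difference is (z for alpha + 0.842) × √(2/21), with √(2/21) = 0.3086.
- At 0.05: (1.960 + 0.842) × 0.3086 = 0.86 SD.
- At 0.01: (2.576 + 0.842) × 0.3086 = 1.05 SD.

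**The case against.** The best defence is that the SAP sets a per-test threshold and promises nothing about the family. Each test keeps its nominal 5%. There is one primary outcome, the analysis is labelled secondary, it compares participants within one arm of a non-randomized study, and no text says that a positive result here counts as success for TREAT-ON. The five outcomes can be read as five separate questions, for which per-comparison error is defensible if it is disclosed. All of this stands, and it is why a mandatory adjustment would be a matter of preference. It does not explain why results in this family should be called significant with nothing to say how many were tested.

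A second objection is that the analysis is already done, so a new label cannot change the error rate of completed tests. That is true. What the label changes is the claim made from them.

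A reader might be tempted by stronger readings that the documents do not support:
- *That the SAP's error rate is inflated from a promised 5%.* No family-wise rate is stated, so none is breached.
- *That one figure, such as 18%, is the rate.* For five tests that value needs an assumed correlation of about 0.5.
- *That there are really 15 tests, five outcomes at three follow-up visits.* The Protocol does say "Data were collected at baseline and 3, 6 and 12 months for all outcome measures except for intervention acceptability", but that is a schedule of data collection. The SAP describes mixed models over time and does not prescribe separate tests by visit.
- *That the small sample drives the problem.* The 42 participants limit power and precision, but not the family-wise rate.

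**Conclusion.** The concern holds as a reporting weakness in a secondary analysis. Five outcomes are each called significant on an unadjusted P-value. With no true differences, at least one such call would appear with probability of about 23% under independence, falling to about 10% at an assumed common correlation of 0.9. The figure rests on one two-sided test per outcome. The conclusion does not depend on the exact correlation: the rate stays above 5% for anything short of perfect correlation.

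This is a cheap improvement worth making and not a flaw in the trial's main result.

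**What to change.** Amend the significance sentence in the SAP's final paragraph along these lines:

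> The two-sided 0.05 significance rule applies to the propensity-matched HbA1c comparison. Comparisons of participants who did and did not meet their goal (HbA1c, self-care, diabetes distress, empowerment, TUQ; one test per outcome) are exploratory. They are given as estimates with 95% confidence intervals, and none is called statistically significant on an unadjusted P-value.

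Because both documents are in the past tense and the analysis set is already known, the report should say that this labelling was adopted after the analysis.

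If the investigators prefer to keep significance claims here, the alternative is Holm across the five outcome-level P-values, with the adjusted values reported. Holm would deal only with the number of tests. It would not settle any question about the grouping itself.

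Cost: wording, or a short step on P-values that already exist, with no new data or participants. The exploratory route loses no precision but gives up significance claims for this family. Under Holm, an isolated result between 0.01 and 0.05 can no longer be called significant, and the detectable difference at the strictest step rises from about 0.86 to 1.05 SD on an even split.
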